### Theme 1: Applying rTMS treatment and its evaluation by neuropsychological and clinical assessments

1. Recruit people (from Riverview Health Center and also from [name] referrals), who have had a head injury within the past two to 12 months, have a clear diagnosis of TBI, and have persistent post-TBI symptoms. Collect standard neuropsychological assessment data at baseline.

2. Enroll the study participants into a “Sham Group” and a “Treatment Group” with a three-week protocol, and apply the treatment.
3. Record spatio-temporal assessments before and after treatment sessions, and examine the efficacy of rTMS treatment on the post-TBI symptoms by standard clinical and neuropsychological assessments by statistical analysis.

Theme 2: Monitoring treatment efficacy by objective measures, EVestG and spatio-temporal assessments

4. Record EVestG data with all its seven current stimuli at baseline (before the treatment) and immediately after treatment and also four and eight weeks after the last treatment.
5. Analyze EVestG data for extracting the optimum measures (biofeatures) showing the changes due to rTMS treatment.
6. Optimize (reduce the number of stimuli if possible) the EVestG recording protocol upon the results of Objective 5.
7. Examine the statistical correlation of the EVestG biofeatures representing the TBI recovery with data from the clinical and neuropsychological assessments as well as spatio-temporal assessments (derived in Objective 3).

Theme 3: Evaluating the objective measures of EVestG and spatio-temporal assessments in Control group

8. Recruit 20 age-and-gender-matched individuals with no history of head injury and record their EVestG data four times with a similar schedule to that of TBI patients, and investigate the consistency of the EVestG data between the sessions and compare with those of people with TBI during treatment.
9. Run the spatio-temporal assessments at the same sessions of EVestG recording in the Control Group and examine the effect of learning on the performance in these assessments.

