### **Study Protocol**

#### **Study Population/Participants**

A total of 20 individuals with a clear diagnosis of TBI within the last 12 months (as confirmed by their treating Neurologist, Psychiatrist or Medical Rehab Physiatrist, who are the co-investigators in this study) prior to the commencement of this study will be recruited from Riverview Health Center patient and [name] clinic patient population. Ten patients will be randomly assigned to **Treatment Group** and 10 others to **Sham Group**. Neither the patients, nor the clinical assessors will know the sham versus real treatment group assignment. In addition, as one of the objectives of this study is to evaluate the EVestG assessment as a

diagnostic and monitoring tool, 20 age-and-gender-matched cognitively healthy volunteers will be recruited as controls for the EVestG assessment. The healthy **Control Group**'s participants must not have any history of TBI and also meet other exclusion criteria for patients group listed below.

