### **Standard Neuropsychological and Screening Measures**

The neuropsychological assessments include: Rivermead Post Concussion Symptoms Questionnaire (RPQ) [7,59], Montreal Cognitive Assessment (MoCA) [60], Montgomery Asberg Depression Rating Scale (MADRS) [61] and Stroop tasks [62]. Patients with TBI will go through all above mentioned assessments four times, similar to EVestG assessments. The healthy Control Group will go through only MoCA and MADRS assessments at the beginning of the study and at the last assessment session.

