### **Data analysis**

**EVestG Biofeature Extraction** – The NEER algorithm [52] will be used to locate and extract vestibular neural events. The interval histograms of the neural events are also used to extract the basic statistical properties of the neural firings such as probability density function (pdf), mean and variance, as well as fractal dimension, kurtosis and skewness of the signal. The features extracted from all tilts will be investigated to determine biofeatures specific to a concussion. The extracted biofeatures, e.g. fractal dimension, kurtosis and skewness of the potentials' distribution, from the recorded signal will be compared between Sham and Treatment Groups.

[figure not shown]
**Statistical Analysis, Clustering, Decision Making and Validation** – After data collection, the multivariate Analysis of Variance (MANOVA) statistical test will be run to determine the significant differences of any of the extracted biofeature measures between the sessions and the Control Group and the Treatment and Sham Groups. In all instances, a p-value less than 0.05 is considered significant. Cross correlation analysis will also be used to find the correlation between these measures and the neuropsychological assessments scores. Once the statistically significant features among the groups are found, the classic approach of discriminant analysis with leave-one-out routine (for robust results in small size data) will be run to investigate whether concussion cases can be identified. An important issue to address is the membership assignment of the subjects. Since there may not be confirmed and solid clinical and neuropsychological assessments for the recovery from the TBI post-symptoms, we will also run unsupervised (blind) clustering of the objective measures followed by our recently developed diagnostic decision making algorithm to identify TBI recovery. The diagnostic and monitoring algorithms will be checked with the updated diagnoses of the clinical symptoms (by the referring physician) and the neuropsychological evaluations.

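### The EVestG-by-score correlations of Objective 7 have no lead pair and no multiplicity control, so the chance of a false link exceeds 5% by an amount set by the open number of features

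*Combined protocol and SAP*

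**What the plan says.** The Data analysis section (Statistical Analysis, Clustering, Decision Making and Validation) first describes a MANOVA of the EVestG features across sessions and groups. It then gives the threshold: "In all instances, a p-value less than 0.05 is considered significant". The next sentence is "Cross correlation analysis will also be used to find the correlation between these measures and the neuropsychological assessments scores".

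These correlations serve Objective 7 (Objectives, Theme 2), which also brings in the spatio-temporal test: "Examine the statistical correlation of the EVestG biofeatures representing the TBI recovery with data from the clinical and neuropsychological assessments as well as spatio-temporal assessments".

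The quantities that set the number of correlations are spread over several sections:

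- **Features.** The Data analysis section gives "fractal dimension, kurtosis and skewness of the potentials" as examples, so the list is open. It adds: "The features extracted from all tilts will be investigated to determine biofeatures specific to a concussion". Objective 4 refers to seven stimuli.
- **Scores.** RPQ, MoCA, MADRS and Stroop, plus the spatio-temporal assessment (Table 1).
- **Visits.** "Patients with TBI will go through all above mentioned assessments four times, similar to EVestG assessments".
- **Patients.** "A total of 20 individuals with a clear diagnosis of TBI within the last 12 months", split 10 and 10.

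No section names a primary outcome, a lead feature-score pair, the visit or change score to be correlated, the number of correlations, or any adjustment for multiplicity. The trial is called a pilot, but the correlations themselves are not called exploratory.

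**The concern.** One threshold applied to a grid of correlations of unstated size gives no control over the chance that some pair passes by luck. The proposal wants EVestG to serve as an objective measure of recovery, and agreement with the clinical scales is one of the supports for that. If any pair that reaches p<0.05 can be reported as a significant link, that support can be produced by search alone.

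This is a question of family size. It is separate from how repeated visits or arms are modelled within a single correlation, and from the comparison of features between Treatment and Sham.

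**Working it through.** The plan states no error rate, power or number of tests for the correlations, so there is no figure of its own to reproduce.

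**Inputs from the documents:** threshold 0.05 (two-sided assumed; sidedness is not stated); 20 patients; three example features; seven stimuli; four neuropsychological scores plus one spatio-temporal score (assuming one score per instrument); four visits.

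**Independent tests.** The chance of at least one p<0.05 among k tests with no true association is 1 - 0.95^k, and the expected number is 0.05k.

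| Grid | k | Chance of at least one | Expected |
|---|---|---|---|
| 1 feature x 5 scores | 5 | 22.6% | 0.25 |
| 3 x 4 | 12 | 46% | 0.60 |
| 3 x 5 | 15 | 54% | 0.75 |
| 3 x 5 x 4 visits | 60 | 95% | 3.0 |
| 3 x 7 stimuli x 5 | 105 | 99.5% | 5.25 |

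The chance passes 50% at k = 14 (51%).

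**Correlated measures.** Features correlate with each other and so do scores, which lowers these figures. Simulation used normal data, n=20, one visit, no feature-score association, and a common correlation within features and within scores of 0.8 down to 0. The chance of at least one p<0.05 was:

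- 1 feature x 4 or 5 scores: about 11-24%. The top is a simulated value; the exact figure for five independent tests is 22.6%.
- 3 features x 5 scores: about 25-53%.
- 21 features (3 x 7 stimuli) x 5 scores: about 48-100%.
- 420 features x 4 scores: about 82-100%.

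The plan does not give the count of 420. It is 5 statistics x 7 stimuli x 6 segments x 2 ears = 420, and it is an upper scenario.

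More visits raise the figures. One feature, four scores and three change visits (12 tests at correlation 0.5) give 34%. For the 60-test grid, correlation of 0.5 / 0.7 / 0.9 within features, scores and visits gives 87% / 70% / 35%.

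**Role of sample size.** For 12 independent tests the simulated chance is about 46% at n = 20, 40 and 200, so n does not drive it. What n sets is the critical value, |r| = t / sqrt(n - 2 + t^2), with t on n - 2 degrees of freedom. At 0.05 this is 0.444 for n=20 and 0.312 for n=40.

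**Cost of control.** At n=20 the critical |r| is 0.444 at 0.05 and 0.499 at 0.025. Under Bonferroni it is 0.623 for 15 tests, 0.708 for 105 and 0.794 for 420 x 4 = 1,680. With three visits and the spatio-temporal score, 420 x 5 x 3 = 6,300 tests give about 0.82. Approximate power at a true r of 0.6, using Fisher's z with atanh(0.6) x sqrt(17) = 2.858:

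- At 0.05: 2.858 - 1.960 = 0.898, so about 82%.
- At 0.025: 2.858 - 2.241 = 0.617, so about 73%.

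**The case against.** **The rule may not reach the correlations.** The p<0.05 sentence follows the MANOVA and precedes the correlation sentence, which does not mention testing. A reader might infer that the plan explicitly tests every correlation at 0.05. The text does not say that. But its wording covers all instances, no other threshold is given, and Objective 7 asks for a statistical correlation, so the inference is strong.

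**The family may be small.** Objective 7 covers only features that represent recovery, after Objective 5 picks the best measures and Objective 6 trims the stimuli if possible. This rightly makes 420 an upper scenario. It does not control the error, because the features are chosen from the same data and neither their number nor the selection rule is fixed. Even one surviving feature exceeds twice the nominal 5%.

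**It is a pilot, and EVestG has other support.** The plan adds leave-one-out discriminant analysis, unsupervised clustering, a check against updated physician diagnoses, and repeat recordings in controls. These are other evidence, so the correlations are not the whole case. None of them protects the correlations, however, and leave-one-out applies to the discriminant analysis only. Pilot status limits the gravity. Yet the Proposal Summary promises a dependable means of diagnosing TBI and monitoring recovery, which is more than hypothesis generation.

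**Conclusion.** The point holds in conditional form. The false-positive chance for Objective 7 is uncontrolled and above 5% in every scenario examined: about 11-24% for one feature, 25-53% for the three example features against five scores, and 48-100% for three features over seven stimuli, at one visit. These figures assume two-sided tests, one score per instrument, no true association and within-set correlation between 0.8 and 0.

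Two stronger readings are tempting and are not supported. The first is that a false link is likely whatever is done. That depends on a feature count the plan does not give, and it fails for one feature, and for three features at one visit once the measures are moderately correlated. The second is that having only 20 patients causes the problem. It does not; small n only makes each chance link look strong and makes correction expensive.

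This should be changed, but it is an ordinary multiplicity gap in a pilot and not a fatal flaw.

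**What to change.** Replace the blanket threshold for the correlation analysis with three rules.

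1. **One deciding pair.** Before any feature-score data are examined, the investigators name one feature, one score and one interval for Objective 7, for example change from week 0 to week 4 in one biofeature against change in RPQ. At most, name two features, each tested at 0.025. Locking before unblinding is not enough, because a pooled correlation can be inspected without the allocation code. Handle arm as in rule 2, by within-arm permutation or an arm-adjusted partial correlation.
2. **One family for the rest.** Test all other feature-by-score-by-visit correlations, including the spatio-temporal score, with a within-arm max-|r| permutation test at family-wise 0.05. Shuffle each patient's whole set of scores together so that the correlations among scores and among features are kept.
3. **Labelling.** Call anything that passes only unadjusted p<0.05 exploratory. Report it with its confidence interval and the number of correlations examined, and do not cite it as evidence that EVestG monitors recovery.

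The change needs analysis-plan wording and a short program, with no new patients or visits. The price is sensitivity. With two deciding features the critical |r| rises from 0.44 to 0.50, and power at a true r of 0.6 falls from about 82% to 73%; one deciding pair avoids that loss. In the upper scenario of 420 features and four scores at one visit, the family-wise critical |r| is about 0.72-0.79. With three visits it reaches about 0.82 under Bonferroni. Most secondary correlations will therefore be exploratory, and a shorter feature list fixed in advance would reduce that cost.

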### **EVestG Measurement**

All study participants (in all three groups) will go through four sessions of EVestG assessments: 1) before rTMS treatment, 2) after 12 sessions of rTMS treatment, 3) four weeks after the last rTMS treatment, and 4) eight weeks after the last rTMS treatment.

The subjects sit in a hydraulic chair with their eyes closed and head rested on the chair headrest; they receive a series of orthogonal passive whole body movement stimuli: up/down translation and a horizontal rotation to the right and return to center (RTC) in both sitting upright and supine positions, and side tilts to the right and left.

Each tilt and the rotation are about 40 degrees, while up/down movement are about eight inches; the movements are designed to be smooth with a constant acceleration/deceleration over 3s. The recordings are made in an acoustically attenuated (>30dB) and electromagnetically shielded chamber at the EVestG Lab, Riverview Health Center. The active gelled recording electrodes are TM-EcochGtrode (Bio-logic, France), and placed in both ears proximal to the eardrum. Reference electrodes (Biopac EL254S for earlobe and EL258S for forehead) are placed on the ipsilateral earlobes and a common ground electrode is placed on the forehead.

The left and right ears' signals are recorded using Spike2 software via a CED-1902 amplifier (60Hz notch filter, 10k gain, 1Hz high pass filter) and digitized using CED1401 ADC board at sampling rate of 41,666Hz. Each recording's duration was 60s for each stimulus: 20s stationary at the center position, 3s motion to a position (up or rotated), 17s stationary in that position, 3s return to the center, and another 17s of stationary recording in the center position.

The chair's position is also recorded simultaneously with the ear signals; it is used to extract the segments of interest for analysis. The particular segments of interest, shown in Figure 2, are: 1.5s immediately prior to the movement (BGi), 1.5s acceleration (onAA) and 1.5s deceleration (onBB) as well as the 1.5s segments from the return to the center: RTC BGi, RTC onAA and RTC

onBB. The acceleration/deceleration segments are selected as they give the largest differences compared to background. Each EVestG recording may take up to one hour.

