**Table 1: Treatment and Assessment Schedule**

Study Groups	Week	# of Treatments	Assessments
Treatment and Sham Groups	0 (Baseline)	None	EVestG, MoCA, MADRS, RPQ, Stroop, and spatiotemporal
	1	5 – Monday to Friday	None
	2	5 – Monday to Friday	None
	3	2 – Mon/Wed or Tue/Thu	None
	4		EVestG, MoCA, MADRS, RPQ, Stroop and spatiotemporal
	8		EVestG, MoCA, MADRS, RPQ, Stroop, and spatiotemporal
	12		EVestG, MoCA, MADRS, RPQ, Stroop, and spatiotemporal
Healthy Control Group	0		EVestG, MoCA, MADRS
	1		
	2		
	3		
	4		EVestG
	8		EVestG
	12		EVestG, MoCA, MADRS

**Figure 1.** Separation of mTBI and control subjects using two post potential features.

**Figure 2.** A) Sitting up/down movement, supine up/down movement, sitting horizontal rotation. B) Ear Electrode; C) Electrode placement; D) Subject connections.

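### EVestG features are screened at an uncorrected p<0.05 on all subjects before leave-one-out classification, so the reported accuracy for identifying concussion is biased upward

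*Combined protocol and SAP*

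**What the plan says.** Under Data analysis (Statistical Analysis, Clustering, Decision Making and Validation), a MANOVA is run once data are collected to find "significant differences of any of the extracted biofeature measures between the sessions and the Control Group and the Treatment and Sham Groups". The threshold is common to everything: "In all instances, a p-value less than 0.05 is considered significant". Classification follows: "Once the statistically significant features among the groups are found, the classic approach of discriminant analysis with leave-one-out routine" is applied to see whether concussion cases can be identified, and leave-one-out is justified by the small sample. The section ends with a check: "The diagnostic and monitoring algorithms will be checked with the updated diagnoses of the clinical symptoms" and the neuropsychological evaluations.

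The pool of candidate features is broad. Objective 4 (Theme 2) reads "Record EVestG data with all its seven current stimuli at baseline" and at the three later sessions. EVestG Measurement records both ears and names six segments per recording: "1.5s immediately prior to the movement (BGi), 1.5s acceleration (onAA) and 1.5s deceleration (onBB) as well as the 1.5s segments" for the return to centre. Data analysis lists several statistics per signal, including mean, variance, fractal dimension, kurtosis and skewness. The total number of candidates is not given.

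Study Population/Participants states that "one of the objectives of this study is to evaluate the EVestG assessment as a" diagnostic and monitoring tool, and the 20 healthy controls are recruited for that purpose.

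**The concern.** Leave-one-out accuracy is honest only if the left-out subject played no part in building the classifier. Here the features are chosen first and leave-one-out is applied afterwards. A feature that separates the groups by chance in these 40 people passes the screen because of those people, and each of them is then classified with it. Refitting the discriminant weights in each fold removes the optimism from fitting but leaves the optimism from selection.

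Nothing in the plan offsets this. It describes no nested selection, feature list fixed in advance, multiplicity adjustment or separate validation sample. The accuracy is the planned evidence on whether EVestG can identify concussion, and as designed it can look well above chance when EVestG carries no information.

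**Working it through.** The plan gives no expected accuracy, candidate count or sample-size calculation for this analysis, so there is no figure of its own to reproduce. The bias was measured by simulation under the null.

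**Inputs from the documents.** 20 TBI patients (10 Treatment, 10 Sham) and 20 controls, so chance accuracy is 50%. Seven stimuli, two ears, six segments. Screen at p<0.05.

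**Assumptions.** The candidate count at one session was taken at two levels:
- 3 statistics x 7 stimuli x 2 ears = 42
- 5 statistics x 7 stimuli x 2 ears x 6 segments = 420

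Features were Gaussian with no group difference. Correlation was 0, 0.5 or 0.7 in blocks of six, or 0.7 across all versions of the same statistic. The screen was an F test on two groups (20/20) or three (10/10/20). The best two, best five or all significant features were kept and passed to linear discriminant analysis with leave-one-out. The contrast between sessions was not modelled. There were 500-1000 runs per setting with the screen outside the folds and 150-500 with it nested.

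**False features to expect.** The expected number is 0.05 x K: 0.05 x 42 = 2.1 and 0.05 x 420 = 21. If features are independent, the chance of at least one is 1 - 0.95^42 = 0.88, and practically 1 for K = 420.

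**Mean leave-one-out accuracy with no true signal, given that at least one feature passes:**

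| Setting | Three-group screen | Two-group screen |
|---|---|---|
| 42 candidates | 60-64% | 63-69% |
| 420 candidates, correlation 0-0.7 in blocks of six | 67-77% | 72-83% |
| 420 candidates, 0.7 across each statistic | 57-63% | 56-68% |
| Best two features only | 60-68% | 65-75% |

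The last row is included because the Figure 1 caption describes "Separation of mTBI and control subjects using two post potential features". With 42 candidates and the three-group screen, no feature passes in 10-42% of runs. A repeat that counted such runs as 50% still gave 56-82%.

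**Screen nested in the folds** (folds with no passing feature scored 0.5): 48-52%. The excess therefore comes from selecting outside the folds.

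**How often a null result would look convincing.** For a binomial with 40 trials and probability 0.5, P(X >= 27) = 0.019, or 0.038 two-sided. With the screen outside the folds, 27/40 or better occurs in 20% to nearly 100% of null runs in which a feature passes; over all null runs the lower end is about 13%. An accuracy of 85% is reached in 0-2% of null runs with 42 candidates. With 420 it is reached in 0-21% (three-group) or 0-46% (two-group). Even when nested, 27/40 or better occurs in 5-17% of runs, so the binomial p-value is not valid for the nested estimate either.

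**Wider range of candidates.** With 3 to 504 candidates, counting runs with no selected feature as 50%, the mean runs from about 51% (three to six candidates) to about 86% (best 10 of 504 independent features).

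**The case against.** The strongest objection is that the plan names MANOVA, not separate tests on each feature, and that a joint test protects the screen. One MANOVA over all candidates could not be computed at a single session with 42 features, since 40 subjects in three groups leave 40 - 3 = 37 error degrees of freedom. But 42 is an assumed count, and a MANOVA per stimulus or on a shorter list is feasible. With seven per-stimulus MANOVAs of six features each, the discriminant step is reached in 21-29% of null runs, the mean counting unreached runs as 50% is 53-56%, and 27/40 or better occurs in 9-20% of all null runs. With a single gate on 6 or 21 features the step is reached in only about 4% of null runs. This part stands: a gate makes the problem rarer. It does not remove it, because accuracy once the step is reached is still 63-69% in the first case and 69-71% in the second. The plan describes no such gate and looks for differences in any of the measures.

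Other points stand in part:
- That the screen uses all subjects is inferred from the order of the text. It is the natural reading and nothing contradicts it.
- The top of the range needs hundreds of independent features, which is unlikely for adjacent segments of one recording.
- The plan sets no accuracy target; 27/40 and 85% are yardsticks only.
- The trial is a pilot, and this output is exploratory.

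The check against updated diagnoses is no defence, because it uses the same participants. The unsupervised clustering is aimed at recovery and does not correct this accuracy.

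**Conclusion.** The concern holds. Followed in the order written, the plan gives a leave-one-out accuracy that is biased upward. The direction does not depend on the assumptions, but the size does: about 56-83% on average with no true signal over the main settings, less with a handful of candidates or a MANOVA gate. The figures rest on assumed candidate counts, correlations and forms of screen, and on one session at a time.

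This should be corrected before the EVestG data are analysed, because the accuracy bears directly on a stated objective and on the reason the control group is recruited. The comparison of active with sham rTMS on the clinical and neuropsychological scales is not touched.

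**What to change.** Change the Data analysis section to say that:
- the feature screen is repeated from scratch inside every leave-one-out fold, using only the remaining subjects;
- all sessions of the left-out subject are held out together;
- the p-value for accuracy comes from permuting the TBI/control labels and rerunning the whole pipeline, screen included, not from a binomial test.

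The text should also list the candidate features, state the form of the screen, and say how a fold with no passing feature is scored, so that the procedure can be rerun exactly.

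The cost is a few lines of analysis text and some computing time, with no new patients, visits or recordings. The price is a lower reported accuracy than the present order would tend to give.

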## Introduction

### a. Rationale

Traumatic brain Injury (TBI) occurs when a sudden trauma causes either transient or permanent brain damage. In some literature, the term “concussion” is used to refer to the most common (mild) type of TBI. It is defined as an immediate and transient impairment of neural functions, such as the alteration of consciousness, balance and/or visual disturbances, due to a direct blow to the head or after a blow elsewhere that is transmitted to the head. In other literature, mostly neurological journals (and in this proposal), mild TBI (mTBI) and concussion are used interchangeably.

Every three minutes, there is a TBI case in Canada [3], and 50,000 Canadians sustain brain injuries each year [4]. Motor vehicle crashes and traffic-related incidents are major causes of TBI; 40% of TBI cases in Manitoba are due to car accidents [5]. Transport Canada reports that the road accident rate of the province of Manitoba is greater than the national average [6]. According to MPI’s 2011/12 annual report, there was an 89% increase in brain injury claims from 146 in 2010/11 to 276 in 2011/12 [5].

The majority of patients with mTBI recover in the first 2-4 weeks; the recovery time is much longer (a few years) for those with severe TBI. In general, the fastest improvement occurs in the first six months after injury and the patient may continue to get better over a period of up to two years. However, many survivors of severe TBI and mTBI continue to experience disabling persistent post-TBI symptoms including somatic and emotional symptoms (sleep disturbances, fatigue, headache and emotional changeability) [7], as well as cognitive [8,9], visual [10-15], and vestibular abnormalities [16,17]. Any of these adverse consequences of TBI impact the individual's quality of life and functionality for years after the injury. In fact, half of the hospitalized TBI patients develop TBI-related long-term or permanent disability [18], and over 70% of people diagnosed with severe TBI require long-lasting care and support [19]. In addition, TBI is strongly associated with subsequent disabling neurological disorders including Alzheimer's and Parkinson's diseases [20].

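### The plan does not say which sessions' EVestG recordings enter the analysis that identifies concussion, and it lets session and treatment effects choose the features for it

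*Combined protocol and SAP*

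**What the plan says.** The section Study Population/Participants makes evaluation of EVestG, for both diagnosis and monitoring, an objective of the study and the reason for recruiting 20 healthy controls. Under EVestG Measurement, "All study participants (in all three groups) will go through four sessions of EVestG assessments". The schedule begins "1) before rTMS treatment, 2) after 12 sessions of rTMS treatment, 3) four weeks after the last rTMS treatment", and the fourth session is eight weeks after the last treatment. Table 1 places the sessions at weeks 0, 4, 8 and 12.

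The analysis is given only in the Data analysis section, under Statistical Analysis, Clustering, Decision Making and Validation:

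- After data collection, a MANOVA looks for differences in the biofeatures "between the sessions and the Control Group and the Treatment and Sham Groups", at p < 0.05.
- The classifier follows: "Once the statistically significant features among the groups are found", a "discriminant analysis with leave-one-out routine (for robust results in small size data) will be run to investigate whether concussion cases can be identified".
- The plan then raises group membership as a problem: "Since there may not be confirmed and solid clinical and neuropsychological assessments for the recovery from the TBI post-symptoms". In response it adds unsupervised clustering and a decision algorithm aimed at recovery. It also checks the algorithms against updated diagnoses and the neuropsychological results.

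Nothing states which session's recordings the discriminant analysis uses, what label a patient's later recording carries, or whether the unit left out is a recording or a person.

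**The concern.** Whether EVestG separates people with TBI from people without is a different question from whether it tracks recovery. At week 0 the first question is clean: a physician has confirmed the TBI, persistent symptoms are required for entry, and nobody has had study rTMS. At later sessions half of the patients have had active rTMS and all have had more time to recover. The Rationale says that "the fastest improvement occurs in the first six months after injury" and that improvement may go on for up to two years. Patients enter 2 to 12 months after injury, so some change during a 12-week study is to be expected.

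Two things are at stake.

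- **Labels.** A recovered patient's recording still labelled TBI lowers apparent sensitivity. A direct effect of rTMS on the signal could instead raise it. The resulting accuracy would describe neither detection of concussion nor recovery.
- **Features.** A feature can be significant in the MANOVA because it changes between sessions or responds to rTMS. As written, such a feature could be carried forward as a marker of concussion.

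Leaving the session open also means that it can be chosen after the accuracies have been seen.

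**Working it through.** The plan gives no target accuracy, effect size or sample-size derivation for this analysis, so there is no figure to reproduce. The check is a count from the stated design, followed by illustrations under assumed values.

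**1. Count of recordings if all sessions were used.** Inputs: 10 Treatment, 10 Sham and 20 Control participants (Study Population/Participants), with four sessions each (EVestG Measurement).

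- TBI recordings: 20 × 4 = 80. Control recordings: 20 × 4 = 80. Total: 160 from 40 people.
- TBI at week 0: 20 of 80 (25%).
- TBI after active rTMS: 10 × 3 = 30 of 80 (37.5%).
- TBI after sham: 10 × 3 = 30 of 80 (37.5%).

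Natural recovery after baseline could affect up to 60 of 80 TBI recordings, and active rTMS up to 30.

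**2. Which data choose the features.** The MANOVA is run after data collection and compares sessions as well as groups. Objective 8 likewise compares controls with people with TBI during treatment. Treatment and Sham are formed by randomisation, so at week 0 they differ only by chance. A genuine difference between them can arise only after treatment has begun. Followed as written, the selection step is open to treatment and session effects.

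**3. Effect of label dilution (illustration).** Assume sensitivity Se = specificity Sp = 0.85. The Background section quotes pilot values above 85%, but after a list of other disorders and for ages 40 to 50, so the figure is not specific to TBI. Let r be the share of later TBI recordings that look like controls. The documents give no value for r.

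With a rule held fixed:

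apparent sensitivity = [20·Se + 60·((1 − r)·Se + r·(1 − Sp))] / 80

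With Se = Sp = 0.85 this is 0.85 − 0.75r × 0.70. Specificity stays at 85%.

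A discriminant analysis would refit its cut-off to the pooled data. With one normal feature, Se = Sp = 0.85 puts the group means 2 × 1.036 SD apart. With m = 0.75r, the refitted midpoint lies at c = 1.036·(1 − m). Then specificity = Φ(c), and apparent sensitivity = (1 − m)·Φ(2.073 − c) + m·(1 − Φ(c)).

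| r (assumed) | Sensitivity, fixed rule | Sensitivity, refitted | Specificity, refitted |
|---|---|---|---|
| 0 | 85% | 85% | 85% |
| 20% | 74.5% | 78% | 81% |
| 30% | 69% | 74% | 79% |
| 50% | 59% | 67% | 74% |

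At r = 50%, average accuracy is about 72% with the fixed rule, (58.75 + 85)/2, and about 71% with the refitted one, (67.4 + 74.1)/2. Refitting moves the loss between sensitivity and specificity but does not remove it. Taking Se = Sp from 0.80 to 0.90 moves the fixed-rule sensitivity at r = 50% only between 57.5% and 60%.

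**4. Unit left out (illustration).** In a simulation, features with no diagnostic value were given to 20 v 20 persons with four recordings each and an assumed within-person correlation of 0.7 (300 runs, linear discriminant). Leaving out single recordings gave about 55%, 58% and 63% accuracy with 2, 5 and 10 features. Leaving out whole persons gave about 50% in each case. This applies only if recordings are pooled and left out one at a time, which the plan does not say.

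**5. Precision at week 0 only.** With 20 TBI patients, 17/20 correct (85%) has an exact (Clopper-Pearson) 95% interval of 62% to 97%.

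**The case against.** The strongest reply is that the plan is silent on the session and does not commit itself to pooling. A baseline-only or session-by-session discriminant analysis would fit the text equally well. The worry about membership is attached to a separate step, the clustering aimed at recovery, which must use later recordings. The section closes by treating diagnostic and monitoring algorithms as distinct, and its reference to subjects and cases suggests persons as the unit. The check against updated diagnoses brings in current clinical status. Finally, this is a pilot, and the rTMS versus sham comparison is untouched.

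Much of this stands. A reader might infer that the classifier will certainly mix treated and untreated recordings, or that single recordings will be left out. The documents support neither inference. The membership sentence alone does not show that later recordings enter the supervised step.

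The reply does not dispose of two points. The feature-selection step is described, not left silent, and it spans sessions and all three groups, so even a week-0 classifier would inherit features chosen partly on later data. Clustering is a separate analysis, and the comparison with updated diagnoses comes afterwards. Neither settles which recordings train the classifier or how they are labelled.

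**Conclusion.** The point holds as a gap that permits mixing, not as proof that mixing is planned. The session and the labelling rule for the discriminant analysis are unspecified, and the described feature selection is open to treatment and session effects. Up to 60 of 80 TBI recordings, 30 of them after active rTMS, could enter under a TBI label.

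The count follows from the design. The accuracy losses and the leakage figures are illustrations. They rest on an assumed r, an assumed 85% that is not specific to TBI, and an assumed within-person correlation of 0.7, so they should not be read as forecasts.

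Week 0 is free of study rTMS but not of all recovery, since patients are already 2 to 12 months past injury. It is nevertheless the one session at which the TBI label and current symptoms are confirmed by the entry criteria. The matter affects the interpretation of the EVestG diagnostic objective only. It is worth correcting because the correction is cheap.

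**What to change.** Add to the statistical paragraph of the Data analysis section:

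- The diagnostic analysis is TBI (Treatment and Sham combined) versus Control, using only each participant's week-0 recording (20 v 20).
- Feature selection for that analysis also uses week-0 recordings only, and is repeated inside each leave-one-out step.
- Weeks 4, 8 and 12 are analysed separately as monitoring. One reasonable way is to apply the week-0 rule unchanged and report whether scores move towards control values, by Treatment and Sham.
- Wherever repeated recordings enter a cross-validated model, all recordings of a participant are left out together.

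The clustering and the check against updated diagnoses can stay as part of the monitoring analysis.

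The cost is a few sentences and no new data. The classifier is trained on 40 recordings instead of up to 160, and the accuracy estimate should be reported with an interval as wide as the one shown above. The loss is smaller than the counts suggest, because the 160 recordings come from the same 40 people.
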